3.7.2.1 Crohn's Disease Activity Index

The CDAI ([Appendix 2](#)) is a composite measurement of disease activity of Crohn's, and is a marker of severity of the subject's condition.¹⁴ The CDAI will be used to assess the primary endpoint of this trial. Some components of the CDAI will be reported by the investigator (physical examination for the presence of an abdominal mass and extraintestinal complications, laboratory results for hematocrit levels, and weight) while other components of the CDAI will be determined with data collected in a subject diary (number of liquid or soft stools, number of antidiarrheal medications, abdominal pain score, and general well-being). The CDAI score at screening will be calculated using the formula in eSource for eligibility. Further details will be provided in a study manual.

Protocol 341-201-00004

3.7.2.2 Simple Endoscopic Score for Crohn's Disease (SES-CD)

The SES-CD ([Appendix 3](#)) is a total score that indicates endoscopic disease activity status based on endoscopy results regarding the size of ulcers, surface ulceration, affected surface size, and presence of luminal narrowing.¹⁵ A decrease of 50% of the SES-CD score is prognostically significant. The SES-CD, supported by histology readings, will be used to assess the secondary efficacy endpoints in this trial. Further details will be provided in a study manual.

3.7.2.3 Two-item Patient Reported Outcome (PRO-2)

The PRO-2 is a symptom control measure based on 2 patient-reported components (stool frequency and abdominal pain) of the CDAI. Further details will be provided in a study manual.

3.7.2.4 Subject Diary

An electronic daily diary will be completed by subjects throughout the trial to record data for the following:

- Patient-reported components of the CDAI score and PRO-2 (stool frequency and number of liquid or soft stools, number of antidiarrheal medications taken, abdominal pain score, and general well-being)
- Presence of visible blood in the stool
- Assessments related to stool sample collection (eg, alcohol intake, list of food and drinks)

Subjects will begin completing the daily diary after signing the consent and will continue completing the daily diary until the 30-day post-treatment follow-up visit.

During the screening period, subjects will be dispensed an electronic diary to complete to collect data for the baseline CDAI assessment. After completion of the diary for 7 days, subjects will undergo bowel preparation for 3 days and then an ileocolonoscopy with biopsy will occur (within 7 to 10 days prior to Day 1). Stool frequency during the week of bowel preparation and ileocolonoscopy will not be used; the daily diary will be restarted on Day 1 (after randomization).

Protocol 341-201-00004

3.7.2.5 Investigator Assessments

The investigator will record the following assessments throughout the trial at the appropriate time points:

- Investigator-reported components of the CDAI score (physical examination for assessment of an abdominal mass and extraintestinal complications, laboratory results for hematocrit levels, and weight)
- Endoscopic results for the SES-CD score (ulcers, surface involved by disease, surface involved by ulcerations, and narrowings)

The CDAI score will be calculated using both subject- and investigator-reported data.

3.7.3 Safety Assessments

3.7.3.1 Adverse Events

Refer to [Section 5](#), Reporting of Adverse Events.

3.7.3.2 Clinical Laboratory Assessments

A central laboratory designated by the sponsor will be used for all laboratory testing required during the trial. Clinical laboratory assessments will be performed at the time points specified in [Table 3.7-1](#). The clinical laboratory assessments for this trial are listed in [Table 3.7.3.2-1](#).

Protocol 341-201-00004

Table 3.7.3.2-1 Clinical Laboratory Assessments

Hematology: Hematocrit Hemoglobin International normalized ratio Mean corpuscular hemoglobin Mean corpuscular hemoglobin concentration Mean corpuscular volume Partial thromboplastin time Platelets Prothrombin time RBC count WBC count with differential	Serum Chemistry: Alkaline phosphatase ALT AST Bicarbonate (or carbon dioxide) Bilirubin, total Blood urea nitrogen Calcium Chloride Creatinine Gamma glutamyl transferase Glucose Potassium Protein, total Sodium
Urinalysis: Appearance Color Blood Glucose Microscopic analysis, WBC/RBC counts per high powered field pH Protein Specific gravity	Additional Tests: Urine pregnancy for WOCBP (a positive urine pregnancy test must be confirmed with a serum pregnancy test) FSH (optional; perimenopausal and postmenopausal female subjects only) CMV (optional CMV testing can be done on the biopsy specimen, if clinically indicated) CRP FCP HIV Viral hepatitis B and C serology Stool microbiology testing (eg, for culture, C difficile , O&P) Urine alcohol and drug screen

RBC = red blood cell; WBC = white blood cell.

The total volume of blood to be collected during the trial will be documented in the ICF.

A urine pregnancy test will be conducted in WOCBP prior to trial intervention (at screening and again on Day 1 [baseline]); results must be available prior to the administration of the IMP. If the urine pregnancy test result is positive, the investigator must follow-up with a confirmatory serum pregnancy test. Additional pregnancy tests may be conducted based on local regulatory requirements, as needed.

Only serum chemistries are required at Day 1; however, if there was a significant change (as determined by the investigator) in any of the subject's concomitant medications since the screening visit, hematology and urinalysis are also required. Only hematology is required at Weeks 4, 8, and 10; and only serum chemistry and hematology are required at the 30-day post-treatment follow-up.

Protocol 341-201-00004

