To date, OPS-2071 has been evaluated in humans in 4 completed phase 1 clinical trials and 1 completed phase 2a clinical trial. In the 5 completed trials conducted in Singapore, Korea, Japan, and the UK, there were no deaths and no subject was withdrawn due to an adverse event (AE) related to OPS-2071. In the phase 1 Singapore trial, 1 subject was withdrawn from the trial due to Grade 4 (Common Terminology Criteria for Adverse Events severity grading) serious adverse events (SAEs) of syncope and hemorrhage intracranial and a Grade 1 AE of atrial fibrillation, all of which resolved and were assessed by the investigator as unrelated to OPS-2071. In the phase 2a trial, 1 serious treatment-emergent adverse event (TEAE) of pyrexia of moderate severity was reported for 1 subject with enteric infection. The event resolved and was considered potentially related to the investigational medicinal product (IMP) by the investigator. There were no expected adverse drug reactions as there were no events that occurred in at least 2 subjects and were deemed serious.

In all 5 completed trials combined, the TEAEs that occurred in more than 1 subject in the OPS-2071 group (n = 136) after single-dose administration and at a higher incidence than the placebo group (n = 48) included the following: headache (5 subjects), abdominal pain, gastroenteritis, pharyngitis, blood creatine phosphokinase increased, and epistaxis (each in 2 subjects).

In all 5 completed trials combined, the TEAEs that occurred in more than 1 subject in the OPS-2071 group (n = 90) after multiple-dose administration and at a higher incidence than the placebo group (n = 16) included the following: headache (7 subjects), somnolence (3 subjects), eosinophilia, nausea, neck pain, and epistaxis (each in 2 subjects).

Other TEAEs that were observed included alanine aminotransferase (ALT) increased, aspartate aminotransferase (AST) increased, and blood bilirubin increased, all of which are considered a class effect of quinolones. However, the incidence rate in placebo-treated subjects was higher than in the OPS-2071 group. Across the completed trials, the increased AST events were not consistent; eg, the highest value was approximately 8 times the upper limit of normal (ULN), and that was observed at baseline and decreased to within the normal range in 1 week, while taking OPS-2071. No clear trend on ALT/AST elevation was observed across the completed trials.

Protocol 341-201-00004

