3.7.1.7 Week 8 (± 2 days)

The following assessments will occur at Week 8 (around Day 56):

- Subjects will complete a daily diary (see [Section 3.7.2.4](#))
- Take vital signs (blood pressure, heart rate, body temperature, and respiratory rate)
- Collect a blood sample for hematology
- Measure body weight
- Determine the CDAI score
- Review and record any concomitant medications
- Assess and record any AEs

After the above assessments have been completed, subjects will be dispensed IMP.

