3.7.1.8 Week 10 (± 2 days)

The following assessments will occur at Week 10 (around Day 70):

- Subjects will complete a daily diary (see [Section 3.7.2.4](#))
- Take vital signs (blood pressure, heart rate, body temperature, and respiratory rate)
- Collect a blood sample for hematology
- Measure body weight
- Determine the CDAI score
- Review and record any concomitant medications
- Assess and record any AEs

After the above assessments have been completed, subjects will be dispensed IMP.

Protocol 341-201-00004

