3.7.1.9 Week 12 (+ 2 days)/End of Treatment

The following assessments will occur at Week 12 (around Day 84)/End of Treatment:

- Subjects will complete a daily diary (see [Section 3.7.2.4](#))
- Record the date and time of dose administration in eSource
- Take vital signs (blood pressure, heart rate, body temperature, and respiratory rate)
- Perform a urine pregnancy test for WOCBP (if the urine pregnancy test result is positive, the investigator must follow-up with a confirmatory serum pregnancy test)
- Perform a 12-lead standard safety ECG
- Collect blood samples for PK analysis 1 to 4 hours after the morning dose at the same time as the collection of blood samples for clinical laboratory tests
- Collect blood samples for hematology and serum chemistry, and a urine sample for urinalysis
- Collect a blood sample for the CRP assessment (not needed if CRP is not elevated on Day 1)
- Perform a physical examination (including body weight)
- Determine the CDAI score (for the Week 12 visit, follow the specific assessment as outlined below)
- Collect a fecal sample for the FCP and microbiota assessment (for the Week 12 visit, follow the specific assessment as outlined below)
- All unused IMP will be collected, and final IMP accountability will be performed
- Review and record any concomitant medications
- Assess and record any AEs

The subject must be taking IMP when the following assessments are completed. In order to ensure this occurs, the following schedule must be followed for Week 12 only:

- Collect a fecal sample for the FCP and microbiota assessment approximately 5 days prior to the Week 12 (eg, Day 79) visit date, prior to the bowel preparation and ileocolonoscopy
- Assess the first 3 elements of the CDAI prior to the bowel preparation:
 - Number of liquid or soft stools each day for 7 days
 - Abdominal pain (graded from 0 - 3 on severity) each day for 7 days
 - General well-being, subjectively assessed from 0 (well) to 4 (terrible) each day for 7 days
- The 3-day bowel preparation (consisting of 2 days of dietary modifications and 1 day of cleansing bowel preparation) should be approximately 4 days prior to the Week 12 (eg, Day 80 through Day 82) visit date

Protocol 341-201-00004

- An ileocolonoscopy with biopsy will be conducted up to approximately 1 day prior to the Week 12 (eg, Day 83) visit date. The ileocolonoscopy will be centrally read.
- Determine the SES-CD after the Week 12 ileocolonoscopy has been completed

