3.8.3.3 Documenting Reasons for Treatment Discontinuation

A subject may discontinue IMP for a number of reasons, including those listed below:

- Reasons related to AE:
 - Subject decides to discontinue because of annoyance or discomfort due to a nonserious AE which is not otherwise determined to be an undue hazard
 - Continuing IMP places the subject at undue risk as determined by the investigator (eg, a safety concern that is possibly, probably, or likely related to IMP)
 - SAE
 - Other potentially IMP-related safety concerns or AEs
- Death
- Reasons unrelated to medical condition (provide detail and review AE history with subject)
- Withdrawal of informed consent (complete written withdrawal of consent form)
- Lost to follow-up
- Pregnancy (see [Section 5.5](#))
- Termination of all or part of the trial by the sponsor

Adverse events that are stopping rules to be reported directly to the medical monitor include the following:

- 1) A confirmed prolongation of QTcF with an absolute value > 500 msec or any QTcF interval prolonged 60 msec or greater compared to baseline
- 2) Hemoglobin count of < 8.0 g/dL
- 3) Platelet count of 100000 μ L or less
- 4) Discontinuation of treatment should be considered for liver function test abnormalities if:
 - a) ALT or AST $> 8 \times$ ULN
 - b) ALT or AST $> 5 \times$ ULN for more than 2 weeks
 - c) ALT or AST $> 3 \times$ ULN and total bilirubin $> 2 \times$ ULN or international normalized ratio > 1.5

Protocol 341-201-00004

- d) ALT or AST $> 3 \times$ ULN with the appearance of fatigue, nausea, vomiting, right upper quadrant pain or tenderness, fever, rash, and/or eosinophilia ($> 5\%$)
- 5) New onset *C difficile* or enteric infection
- 6) Any IMP-related clinically significant event that jeopardizes the safety or health of the subject
- 7) Any IMP-related clinically significant event, uncontrolled by optimal medical care
- 8) Any toxicity related to IMP administration, requiring the delay of administration of IMP > 5 days

If the subject discontinues IMP due to an AE, the investigator, or other trial personnel, will make every effort to follow the event until it has resolved or stabilized. Refer to [Section 3.8.3.2](#) for requirements in the event of IMP discontinuation.

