- Potential serious hepatotoxicity (see [Section 5.4](#)).
- Pregnancies are also defined as IREs. Although normal pregnancy is not an AE, it will mandate IMP discontinuation and must be reported on an IRE form to the sponsor. Pregnancy will only be documented on the AE screen in eSource if there is an abnormality or complication.

Adverse events that are stopping rules to be reported directly to the medical monitor are listed in [Section 3.8.3.3](#).

Clinical Laboratory Test Value Changes: It is the investigator's responsibility to review the results of all laboratory tests as they become available. This review will be documented by the investigator's dated signature on the laboratory report. For each abnormal laboratory test result, the investigator needs to ascertain if this is an abnormal (ie, clinically significant) change from baseline for that individual subject. This

Protocol 341-201-00004

determination, however, does not necessarily need to be made the first time an abnormal value is observed. The investigator may repeat the laboratory test or request additional tests to verify the results of the original laboratory tests. If this laboratory value is considered medically relevant by the investigator (subject is symptomatic, requiring corrective treatment or further evaluation), or if the laboratory value leads to discontinuation, and/or fulfills a seriousness criterion, this is considered an AE.

Severity: Adverse events will be graded on a 3-point scale and reported as indicated in eSource. The intensity of an adverse experience is defined as follows:

- 1 = Mild:** Discomfort noticed, but no disruption to daily activity.
- 2 = Moderate:** Discomfort sufficient to reduce or affect normal daily activity.
- 3 = Severe:** Inability to work or perform normal daily activity.

IMP Causality: Assessment of causal relationship of an AE to the use of the IMP is defined as follows:

- Related*:** There is a reasonable possibility of a temporal and causal relationship between the IMP and the AE.
- Not Related:** There is no temporal or causal relationship between the IMP and the AE.

*Investigators should carefully consider consequences of the bowel preparation when assigning causality of AEs (eg, diarrhea).

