5.4 Potential Serious Hepatotoxicity

For a subject who experiences an elevation in AST or ALT that is ≥ 3 times the ULN, a total bilirubin level should also be evaluated. If the total bilirubin is ≥ 2 times the ULN, complete an IRE form with all values listed and also report as an AE in eSource.

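### No liver tests are scheduled between Week 6 and the last dose at Week 12, so a silent late ALT/AST rise cannot reach the liver stopping rule while it can still change dosing

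*Protocol*

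**What the plan says.** Protocol Table 3.7.3.2-1 lists ALT, AST and total bilirubin under serum chemistry. The hematology panel contains INR and a white-cell differential but no transaminase or bilirubin.

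On-treatment chemistry is scheduled at Day 8, Week 2, Week 6 and Week 12, after a Day 1 baseline sample. For the other visits Section 3.7.3.2 says "Only hematology is required at Weeks 4, 8, and 10". Footnote i to Table 3.7-1 repeats this, and the visit lists agree: the only safety laboratory item at Week 8 is "Collect a blood sample for hematology", and Week 10 is the same.

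At Week 12, Section 3.7.1.9 times the PK sample "1 to 4 hours after the morning dose at the same time as the collection of blood samples for clinical laboratory tests". Footnote s to Table 3.7-1 makes that morning dose the last one.

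Liver stopping rule 4 in Section 3.8.3.3 begins "Discontinuation of treatment should be considered for liver function test abnormalities if" and gives four limbs:
- (a) ALT or AST above 8 x ULN;
- (b) above 5 x ULN for more than 2 weeks;
- (c) above 3 x ULN with bilirubin above 2 x ULN or INR above 1.5;
- (d) above 3 x ULN with listed symptoms or eosinophilia.

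Section 1.3 describes increases in ALT, AST and bilirubin as "all of which are considered a class effect of quinolones".

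**The concern.** A rule that prompts the investigator to think about stopping is useful only if the triggering value arrives while there is dosing left to stop. In the second half of treatment no scheduled test can provide that value.

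The other safeguards do not call for the missing test:
- Section 5.1 says "The investigator may repeat the laboratory test or request additional tests to verify the results of the original laboratory tests". That is discretionary and follows an abnormal result already in hand.
- Section 5.4 says that "a total bilirubin level should also be evaluated", but only once ALT or AST has reached 3 x ULN.
- The data monitoring committee (Section 3.7.9) can review only what has been collected; its charter is a separate document not seen here.
- Symptoms, or an abnormal INR or eosinophil count at Week 8 or 10, might lead an investigator to order liver tests, but nothing requires it.

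Prior human experience does not cover late onset. Multiple dosing in healthy subjects, up to 600 mg BID, lasted at most 7 days (Section 2.2). The longest course in the phase 2a trial was 10 days, at 100 mg BID in 5 subjects (Section 1.2). This trial doses for 84 days, which is 84/7 = 12 times and 84/10 = 8.4 times as long.

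**Working it through.** The documents give no figure to reproduce; the check is schedule arithmetic.

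**Inputs** (Table 3.7-1 and Sections 3.7.1.2 to 3.7.1.9)
- Chemistry days, current: 1 (baseline), 8, 14, 42, 84.
- Chemistry days with Weeks 8 and 10 added: 1, 8, 14, 42, 56, 70, 84.
- Visit windows: Week 6 = Day 40 to 44; Week 8 = Day 54 to 58; Week 10 = Day 68 to 72; Week 12 = Day 84 to 86.
- Last dose: Week 12 morning, nominally Day 84.

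**Gaps between chemistry samples**
- Current, nominal: 8 − 1 = 7; 14 − 8 = 6; 42 − 14 = 28; 84 − 42 = 42. The last is the longest, and 42/84 = 0.5 of treatment.
- Week 6 to Week 12 with windows: 84 − 44 = 40 to 86 − 40 = 46 days.
- Proposed, nominal after Week 6: 14, 14, 14.
- Proposed, with windows: Week 6 to 8, 54 − 44 = 10 to 58 − 40 = 18; Week 8 to 10, 68 − 58 = 10 to 72 − 54 = 18; Week 10 to 12, 84 − 72 = 12 to 86 − 68 = 18.

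**When a persistent rise is first seen.** Take each possible onset day from 43 to 84 (42 days) and assign it to the next chemistry day.

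| Onset day | First scheduled value, current | First scheduled value, proposed |
|---|---|---|
| 43 to 56 (14 days) | Day 84 | Day 56 |
| 57 to 70 (14 days) | Day 84 | Day 70 |
| 71 to 84 (14 days) | Day 84 | Day 84 |

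Onset days with a value before Week 12: 0 of 42 now, 14 + 14 = 28 of 42 proposed. Longest wait: 84 − 43 = 41 days now, 56 − 43 = 13 days proposed. Days are counted equally as an illustration; this is not an incidence estimate.

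**Dosing time left when the result arrives.** The documents give no laboratory turnaround; assume 1 to 7 days.
- Week 8 sample: 84 − 57 = 27 down to 84 − 63 = 21 dosing days left (29 down to 19 with the visit window).
- Week 10 sample: 84 − 71 = 13 down to 84 − 77 = 7 (15 down to 5 with the visit window).
- Week 12 sample: none.

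**The case against.** The schedule is stated consistently and looks deliberate. The Protocol's amendment history shows that Amendment 1 both introduced the liver criteria and clarified that these visits are hematology only, and Amendment 2 reworked the chemistry panel without altering this. That shows the schedule was revisited, but the documents give no reason for omitting liver tests at Weeks 8 and 10.

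The prior evidence is reassuring. Section 1.3 reports no clear ALT/AST trend, a higher rate on placebo, low expected systemic exposure, and no nonclinical finding thought to need monitoring. The animal studies ran 26 weeks in rats and 13 weeks in monkeys. The highest AST in earlier trials, about 8 x ULN, was a baseline value that normalised within a week on drug. Subjects above 1.5 x ULN are excluded. All of this stands and keeps the concern small, but none of it is human data beyond 10 days.

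The exposed slice is also narrower than the whole rule. Limb (d) can be reached through symptoms or eosinophilia, and the INR part of limb (c) is measured at Weeks 8 and 10. Yet both limbs still need an ALT or AST value, and an isolated silent rise relevant to (a) or (b) would give no cue.

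The fix is partial:
- Weeks 8 and 10 are exactly 14 days apart nominally, so two on-schedule values do not satisfy more than 2 weeks in limb (b); that limb would need an unscheduled repeat, which an abnormal Week 8 value would at least prompt.
- Onsets after Day 70 would still first appear at Week 12.
- The 28-day gap from Week 2 to Week 6 would become the longest on treatment.

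Finally, SAP Section 11 reports that the trial ended early with three randomized subjects. That limits the practical use of a change to any later protocol built on this schedule; it does not alter the assessment of the plan as written.

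**Conclusion.** The concern holds, as a low-cost safety improvement rather than an error in the plan. For 42 days (40 to 46 with windows), no limb of rule 4 can be triggered by a scheduled test while dosing continues. This rests on the schedule alone and is certain. It is confined to asymptomatic rises beginning after a normal Week 6 sample and to scheduled testing.

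The number of subjects who would benefit cannot be estimated from the documents. The 0 of 42 versus 28 of 42 comparison describes the calendar, and the dosing days left depend on the assumed 1 to 7 day turnaround.

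**What to change.** Amend Section 3.7.3.2, footnote i to Table 3.7-1, and the Week 8 and Week 10 visit lists (Sections 3.7.1.7 and 3.7.1.8) to add ALT, AST, total bilirubin and alkaline phosphatase, using one extra serum tube at the existing hematology draw. Week 4 can stay as it is: a rise in that interval is seen at Week 6, with 84 − 42 = 42 nominal days of treatment left, less turnaround.

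A Week 8 result could be reviewed before the next supply is handed out, since Section 3.7.1.8 says of Week 10: "After the above assessments have been completed, subjects will be dispensed IMP". The dispensing row of Table 3.7-1, in the copy read here, shows no mark at Week 10, so that should be reconciled. A site can in any case stop dosing by contacting the subject.

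Cost: at most 2 x 240 = 480 central-laboratory panels, and two extra tubes per subject (5 to 10 mL in total at an assumed 2.5 to 5 mL each), to be reflected in the blood volume stated in the consent form. Some incidental elevations will need follow-up. The documents give no rate; at an assumed 0% to 2% of 240 subjects, that is 0 to about 5 subjects. No new visit or venipuncture is needed.
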